## 2.6.2 Determining the Study Sample Size

The study sample size was determined at 240 patients.

In order to achieve representativeness of the sample, strength of evidence, high level of reliability and cost-effectiveness of the study, the minimum sample size calculations were performed using two tools that provided two approximate sample sizes. It is assumed that for the subsequent statistical analysis of the study results for calculating the odds ratio, relative risks and benefits, a larger number of variables would be better, and if the average of these two sizes of the study sample deviates towards the larger one, it was taken as the sample size.

The calculations were performed using the following tools:

### (1) Sample size calculation for scientific studies using a standard calculator\*

According to the population size data, the proportion of the population that may have the demographic characteristics characteristic of the study sample (men and women aged 35-79) is 24%†.

In addition, the size (number) of the population with the clinical characteristics required for the study, from which the sample is directly selected, was calculated based on the rates of new cases of the disease/condition. According to the NCDC data for 2022, there were 2056 new cases registered in the categories of other forms of angina [ICD-10, I20.8] and angina unspecified [ICD-10, I20.9], for which ePCI and subsequent treatment with a P2Y12 inhibitor (clopidogrel or alternative) were likely to be performed‡.

Using this population data and statistical calculations performed with a 95% confidence level and a  $\pm 5\%$  confidence interval for the results, the calculated sample size is a minimum of 251 study participants.

*\* There are no direct, structured data on ePCI performed in men and women aged 40-75 years in Georgia or on the prescription/prescription of clopidogrel or alternative P2Y12 inhibitors in patients with this condition. Therefore, the study sample size was determined by indirect calculation of the data.*

*† According to the 2021 demographic data of the National Statistics Service, the number of men and women aged 40-75 years in the general population of Georgia is 932,000, which is 24% of the general population.*

*‡ Among the eligible new cases of CAD in 2022 by the NCDC, the number of patients registered under the categories of other forms of angina [ICD-10, I20.8] and angina unspecified [ICD-10, I20.9], for whose management post-ePCI treatment with P2Y12 inhibitors is likely, is 2,056.*

## **(2) Sample size calculation for a randomized, parallel, case-control study.**

This tool for calculating the study sample size in a selected population will demonstrate reliable statistical relationships and estimate the effects of factors on the development of disease outcomes. With a two-sided statistical relationship, a confidence interval of  $-\alpha - 0.05$ , a power of  $(1-\beta) - 0.8$ , a case/control ratio of  $-2$ , a probability of developing an event in the case group -  $p_0$  - up to 0.4, and a probability of developing an event in the control group -  $p_1$  - up to 0.6, the calculated sample size is determined as a minimum 221 patients.

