Sample size	
The sample size for the study was determined to be 240 patients.
 
Calculations were made using two instruments that provided two approximate sample sizes. The median of these values (considering that the better the odds ratio could be achieved from the larger the sample size) was taken as the sample size.
 
(1) Calculate the sample size for scientific studies using a standard numerator based on the proportion of the population that is likely to have the demographic characteristics of the study sample and the size (number) of the population with the clinical characteristics expected for the study, with a 95% confidence level and a <math>\pm 5\%</math> confidence interval for the results of the statistical calculations.

	
(2) Sample size calculation for a randomized, parallel case-control study with a two-sided statistical significance level, at a confidence interval of <math>\alpha = 0.05</math>, at statistical power of <math>(1-\beta) = 0.8</math>, at case/control ratio of 2, at probability of occurrence of an event in the experimental arm of <math>p_0</math> – up to 0.4, and at probability of occurrence of an event in the control arm of <math>p_1</math> – up to 0.6.

Data processing	
The study data will be processed in stages when:
 
I - More than 50% of patients are enrolled in the study;
 
II - The study group is fully formed, and by this time, more than 50% of patients have completed the 3-month observation period, and some patients have completed the 6-month observation period.
 
III - all patients included in the study have completed the 6 months, and some have completed the 12 months;
 
IV - All patients included in the study have completed the 12-month observation period.
 
The following will be carried out during the follow-up periods:
 

— Observation of MACCEs and collection of information about them;

— Monitoring and evaluation of the project;

— Observation and analysis of study activities, procedures, non-clinical outcomes and safety data.

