## 2.4 Study Participant Selection

### 2.4.1 General Characteristics of Study Participants

Study participants are patients requiring treatment with clopidogrel or an alternative P2Y12 inhibitor following ePCI as a major cardiovascular clinical event for CAD.

Study participants will be selected based on a clinical model defined by stable CAD confirmed by ePCI. They have undergone coronary stenting within the past 12 weeks to reduce their risk, and despite this reduction, they are still at risk of developing recurrent MACCEs. To reduce the risk of subsequent MACCE, the patient with these clinical characteristics requires antiplatelet therapy with clopidogrel after coronary stenting. Carriers of CYP2C19 \*2, \*3 LOF alleles, as patients at complement risk due to expected resistance to clopidogrel treatment, will be given antiplatelet therapy with an alternative P2Y12 inhibitor to clopidogrel for prevention.

In contrast to primary PCI for the management of CAD STE/NSTE-ACS or coronary artery bypass grafting, patients selected with the study clinical model have a relatively lower risk of developing recurrent MACCEs. By equalizing or excluding complementary cardiovascular risky conditions, and co-morbidities, which will be achieved by using study participants' inclusion and exclusion criteria, precise antiplatelet therapy using P2Y12 inhibitors and ensuring adherence to treatment at baseline the probability of recurrent MACCE cases will be equal for the experimental and control arm of study participants. Thus, it will be possible to follow-up and evaluate the clinical outcomes of CYP2C19 genotype-guided as well as conventional treatment with P2Y12 inhibitors (clopidogrel or alternative) which is the aim of the study.

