## 2.4.2 Expected Number of Study Participants

Patients with stable CAD who have undergone ePCI coronary artery stenting without clinically significant procedural complications, require conventional antiplatelet therapy with a P2Y12 inhibitor, meet inclusion criteria, do not present exclusion criteria, and provide informed consent for participation will be selected and randomized for the study.

The sample size of 240 study participants is determined for inclusion in the study. Calculations were made using two instruments that provided two approximate sample sizes. The median of these values (considering that the greater level of significance of the odds ratio and the relative absolute risk values could be achieved with the larger sample size) was taken as the sample size.

(1) Calculate the sample size for scientific studies using a standard numerator based on the proportion of the population that is likely to have the demographic characteristics of the study sample and the size (number) of the population with the clinical characteristics expected for the study, with a 95% confidence level and a  $\pm 5\%$  confidence interval for the results of the statistical calculations.

(2) Sample size calculation for a randomized, parallel case-control study with a two-sided statistical significance level, at a confidence interval of  $\alpha = 0.05$ , at statistical power of  $(1-\beta) = 0.8$ , at case/control ratio of 2, at probability of occurrence of an event in the experimental arm of  $p_0$  – up to 0.4, and at probability of occurrence of an event in the control arm of  $p_1$  – up to 0.6.

Study participants will be randomly assigned to two parallel groups, control and experimental, with a 1:2 allocation ratio and selected 3 study arms for participants by CYP2C19 genotyping results:

1st arm – experimental: "Normal Metabolizers of Clopidogrel", 110 study participants diagnosed with chronic coronary artery disease who had undergone elective PCI, tested with CYP2C19 genotyping and identified as NFA \*2, \*3 carriers, who undergo CYP2C19 Genotype-Guided Clopidogrel Treatment - Clopidogrel as a component of preventive antiplatelet treatment such as double antiplatelet treatment (DAPT), or an antiplatelet drug (clopidogrel) combined with the non-vitamin K antagonist oral anticoagulants (NOAC), incl. triple antiplatelet treatment (Aspirin, Clopidogrel and a NOAC), or antiplatelet monotherapy (Clopidogrel).

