2nd arm - experimental: "Passive Metabolizers of Clopidogrel", approximately† 50 study participants diagnosed with chronic coronary artery disease who had undergone elective PCI, tested with CYP2C19 genotyping, identified as LOF \*2, \*3 allele carriers, who undergo CYP2C19 Genotype Guided Antiplatelet Treatment Alternative to Clopidogrel - an antiplatelet drug alternative to clopidogrel in conventional dosing regimen, as a component of preventive antiplatelet treatment, such as double antiplatelet treatment (DAPT) with ticagrelor or prasugrel, or prasugrel combined with the nonvitamin K antagonist oral anticoagulants (NOAC), or antiplatelet monotherapy (ticagrelor, or prasugrel).

3rd arm - active comparator: "Unspecified Metabolizers of Clopidogrel", 80 participants diagnosed with chronic coronary artery disease who had undergone elective PCI were allocated to the arm, without CYP2C19 genotyping through simple randomization, and having an unspecified metabolism phenotype, who were assigned to the conventional clopidogrel treatment - clopidogrel as a component of preventive antiplatelet treatment, such as double antiplatelet treatment (DAPT), or clopidogrel combined with the non-vitamin K antagonist oral anticoagulants (NOAC), incl. triple antiplatelet treatment (Aspirin, Clopidogrel and a NOAC), or antiplatelet monotherapy (Clopidogrel).

† The prevalence of carriers of CYP2C19 \*2, \*3 non-functional alleles in the Georgian population has not been studied and is unknown. To estimate the number of patients in subgroup II arm 1 and arm 2, we used the extrapolation of known data from a European population study [12].

2 study arms could be used as control for analyzing and comparing study outcome measures: 3rd study arm participants create the active comparators' group for 1st and 2nd arm, and besides, 2nd study arm participants - as the comparators for 1st arm:

Control 1: "Normal Metabolizers of Clopidogrel" - 110 study participants vs "Unspecified Metabolizers of Clopidogrel" - 80 participants;

Control 2: "Passive Metabolizers of Clopidogrel" - approximately 50 participants vs "Unspecified Metabolizers of Clopidogrel" - 80 participants;

Control 3: "Normal Metabolizers of Clopidogrel" - 110 study participants vs "Passive Metabolizers of Clopidogrel" - approximately 50 participants.

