## **2.6 Evaluation of Study Results**

### **2.6.1 Study Endpoints**

The study follow-up results will be discussed and presented by study arms, as well as concerning the primary and secondary endpoints of the study.

The study results will also be discussed concerning other endpoints, which will be represented by clinical or non-clinical data and characterize the factors that affect the efficacy of antiplatelet treatment and determine the clinical and non-clinical outcome in the course of the CCSs both with and without the results of CYP2C19 genotyping.

The indicators for assessing the effectiveness of the study are presented in Appendix 5.

In the study, the selection of treatment regimens with clopidogrel and an alternative P2Y12 inhibitor will be carried out by determining the genotype of the CYP2C19 \*2, \*3 non-functional alleles. Clopidogrel will be used in study participants with CYP2C19 \*2, \*3 normal allele genotypes and in the control arm of study participants not undergone CYP2C19 genotyping – unspecified CYP2C19 genotype. Study participants with CYP2C19 \*2, \*3 non-functional allele genotypes will be given alternative antiplatelet therapy.

In cases of CAD, regardless of treatment with P2Y12 inhibitors after ePCI, the clinical endpoints will be represented with MACCEs and other clinical conditions related to CAD or the potential adverse events of antiplatelet drug treatment. The incidence of the primary, secondary and other study endpoints defined as clinical outcomes of CYP2C19 genotype-guided P2Y12 inhibitor treatment will be assessed in the study arms.

The primary endpoints of the study are defined as:

- Number of study participants who died from any cause (Death from Any Cause) within a 12-month of the study follow-up;
- Number of study participants who died from any cardiovascular cause (Death from Cardiovascular Cause) within a 12-month of the study follow-up;

The secondary endpoints of the study are defined as:

- Number of study participants who experienced non-fatal myocardial infarction (Non-fatal Myocardial Infarction) within a 12-month of the study follow-up;
- Number of study participants who experienced unstable angina or angina requiring hospitalization (Unstable Angina) within a 12-month of the study follow-up;
- Number of study participants who experienced a stroke or transitory cerebral ischemic event (Stroke or TIA) within a 12-month of the study follow-up;

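### The plan's only power statement (80%, minimum 221) names no event, and the 80% does not hold for the two primary death endpoints

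*Combined protocol and SAP*

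**What the plan says.** Calculation (2) in section 2.6.2 assigns the case group an event probability of "up to 0.4, and a probability of developing an event in the control group", the latter being "up to 0.6, the calculated sample size is determined as a minimum 221 patients". The same inputs appear in the synopsis ("at probability of occurrence of an event in the experimental arm of") and in section 2.4.2 ("at probability of occurrence of an event in the control arm of"). None of the three places says what the event is.

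Section 2.6.1 defines two primary endpoints. One is "Number of study participants who died from any cause (Death from Any Cause) within a 12-month of the study follow-up". The other counts cardiovascular deaths over the same period.

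No expected death rate is given. Section 3.2.1 gives one absolute frequency, 1–10%, for a list of MACCEs that includes cardiovascular death, without a time horizon. Section 2.4.1 contrasts the study group with patients having primary PCI for ACS, "or coronary artery bypass grafting, patients selected with the study clinical model have a relatively lower risk of developing recurrent MACCEs".

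Randomisation is 1:2, control to experimental (sections 2.3.2 and 2.4.2), that is 80 and 160. Section 2.4.2 then says "2 study arms could be used as control for analyzing and comparing study outcome measures" and lists 110 versus 80, about 50 versus 80, and 110 versus about 50. The aggregated contrast, 160 versus 80, appears only in Appendix 3. Section 2.5.7 labels the arms differently: it calls the ungenotyped group experimental and the passive metabolizers the control.

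Section 2.4.2 expects 75% of participants to complete 12 months. Section 2.6.2 bases 240 on calculation (2) and on calculation (1), whose result is 251.

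**The concern.** This is the only power figure in the plan, and it stands with no endpoint attached. A reader will naturally connect it to the primary endpoints, which are deaths. Taken as death rates, 0.4 and 0.6 would mean 0.4 × 160 = 64 deaths in the guided group and 0.6 × 80 = 48 in the control group, in patients the protocol describes as lower risk.

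The synopsis hypothesis is that genotype guidance gives better clinical outcomes, and section 2.6.3 keeps chi-square and Fisher tests. If the 80% is believed, a non-significant mortality result could be taken as evidence of no difference when the trial had little chance of showing one.

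**Working it through.** **1. Reproduce 221.** Inputs from section 2.6.2 (2): two-sided α 0.05, power 0.8, k = 2, p₀ = 0.4, p₁ = 0.6, both read as point values.

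- p̄ = (0.6 + 2 × 0.4)/3 = 0.4667, so p̄(1 − p̄) = 0.2489.
- Control n = (1.960 + 0.842)² × p̄(1 − p̄) × (1 + 1/k)/(p₁ − p₀)² = 7.849 × 0.2489 × 1.5/0.04 = 73.26.
- Total before rounding: 3 × 73.26 = 219.8. Rounded up by arm: 74 + 147 = 221.
- With pooled variance under the null and separate variances under the alternative, the total is 217.4.

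The stated total is correct for these inputs.

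**2. Do the bounds fix the total?** They do not. The second formula gives about 131 for 0.1 versus 0.3 and about 647 for 0.2 versus 0.3. Other pairs inside the bounds also land near 221: the first formula gives 220.7 for 0.06 versus 0.18, 220.8 for 0.18 versus 0.35 and 220.6 for 0.28 versus 0.47. So 221 does not reveal which rates, or which event, were meant.

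**3. Which comparison?** The ratio of 2 and the labels experimental arm and control arm match the randomised 160 versus 80. None of the three comparisons listed in section 2.4.2 is 2:1 experimental to control.

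**4. Power for death, 160 versus 80.** The plan gives no death rate and no target ratio. Assumptions: control mortality 1–10%, borrowed from the MACCE range, and the risk ratio implied by the plan's inputs, 0.4/0.6 = 2/3. Power is exact, by binomial enumeration, two-sided 0.05.

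| Assumed control mortality | Guided mortality at RR 2/3 | Fisher | Uncorrected chi-square |
|---|---|---|---|
| 1% | 0.67% | 2% | 7% |
| 2% | 1.33% | 5% | 8% |
| 5% | 3.33% | 9% | 10% |
| 10% | 6.67% | 13% | 16% |

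As an extreme case, with no deaths at all in the guided group and 5% in the control group, Fisher power is 77%.

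**5. Power at 0.4 versus 0.6** (exact Fisher to uncorrected chi-square):

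| Groups | Power |
|---|---|
| 160 vs 80 (all 240) | 81–84% |
| 120 vs 60 (240 × 0.75 = 180) | 69–72% |
| 110 vs 80 | 75–79% |
| 50 vs 80 | 60–61% |

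No figure is given for 110 versus 50. Both are experimental arms, so the plan's inputs assign them the same probability.

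**6. Non-completion.** Inflating 221 for 25% loss would give 221/0.75 = 294.7. The adopted 240 is close to the mean of the two calculations, (251 + 221)/2 = 236, so no such allowance is in it.

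**7. Calculation (1).** A survey precision formula for a proportion of 24% with a ±5% margin gives 1.96² × 0.24 × 0.76/0.05² = 280.3. Correcting for a population of 2,056 gives 280.3/(1 + 279.3/2,056) = 246.8, close to the stated 251. The small gap does not matter. The 24% is the share of the general population in an age band. It is not an outcome, and the formula compares no groups.

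**The case against.** The best defence is that the plan never claims 80% power for death. Section 2.6.3 makes the primary analysis descriptive and already asks for effect measures with 95% confidence intervals, and no section equates non-significance with no difference. All of this stands. It limits the point to what the power statement can be taken to cover, and it is why no change of sample size follows.

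Five stronger readings are tempting, and the documents do not support them:

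- **The arithmetic is wrong.** It is not; 221 reproduces.
- **221 can arise only from 0.4 and 0.6 exactly.** Step 2 shows other pairs that reach it. The fault is that the bounds leave the total open.
- **No comparison can be identified.** The allocation ratio and arm labels imply 160 versus 80, and Appendix 3 analyses that contrast. It is left implicit and is blurred by the list in section 2.4.2 and the labels in section 2.5.7, but it can be inferred. The event cannot.
- **The listed pairwise comparisons break a promise of 80%.** Section 2.4.2 says only that these arms could be compared and claims no power for them.
- **A quarter of the information is lost.** Section 2.4.2 keeps data from some participants who drop out, and section 2.5.6 allows some non-adherent withdrawals up to the 6-month follow-up to be replaced. The 180 case is a worst case.

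The 0.4 and 0.6 may have been meant for a broad composite. That is possible, but the plan does not say so and cites no source.

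**Conclusion.** The concern holds in this form. The plan's one power statement has no named event, its bounds do not determine a sample size, and its 80% is not a property of the design for the two primary endpoints. At assumed control mortality of 1–10% and a risk ratio of 2/3, Fisher power for 160 versus 80 is about 2–13%.

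Those figures rest on assumed rates and an illustrative ratio, because the document supplies neither. The absence of any support for 40–60% mortality does not depend on them.

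Even for an event that did occur at 0.4 versus 0.6, power is 81–84% with all 240 contributing and could fall to 69–72%. Calculation (1) cannot make up for this, since it does not concern a treatment comparison. The correction is needed because 240 is justified by these two calculations, but it is a correction of wording.

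**What to change.** Amend the synopsis, section 2.4.2 and section 2.6.2. The sample size can stay at 240.

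(a) Name the event to which 0.4 versus 0.6 applies, state that the comparison is the randomised 160 versus 80, and give a source; otherwise withdraw the 80%. In either case, state that it does not apply to the two death endpoints.

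(b) Report the mortality power range for 160 versus 80 as a limitation, with the test named and the rates labelled as assumptions. Interpret mortality through the 95% confidence intervals already planned in section 2.6.3.

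(c) If 0.4 versus 0.6 is kept for a named endpoint, state 81–84% with all 240 and 69–72% at 180 contributors. State also that the two listed comparisons with the control arm fall below 80% (75–79% for 110 versus 80, 60–61% for 50 versus 80). Give no figure for 110 versus 50.

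(d) Do not present calculation (1) as support for a comparative sample size. If expected precision is added, label it supplementary and not the basis on which 240 was set. Use a score-type interval, because event counts are low. For equal assumed rates in 160 and 80, the Newcombe 95% interval for guided minus control is about −6.1 to +3.9 percentage points at 2%, −7.6 to +5.5 at 5% and −9.3 to +7.4 at 10%.

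The cost is wording only, with no added patients. The downside is a much less favourable stated power.

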### **2.6.3 Statistical Analysis of Study Results**

Primary statistical analysis will be carried out using descriptive statistics methods. The values and distribution of quantitative and qualitative variables from the study participants' initial clinical assessment and follow-up results will be evaluated according to the experimental and control arms. The magnitudes and trends of the variations of the data values will be analyzed.

Quantitative variable data will be calculated by mean, standard deviation, and median. For comparative statistical analysis, differences between the variable values will be calculated using the t-test or the Wilcoxon signed-rank test.

Categorical variable data will be calculated as frequencies and percentages (%). For comparative statistical analysis, differences between the variable values will be calculated using the chi-square or Fisher's exact tests.

To analyze the effectiveness of selected study interventions, the frequency of detection of clinical endpoints in the experimental treatment intervention arms (Rt1 and Rt2) and the comparator arm (Rc) will be calculated. According to the frequencies of clinical endpoint-positive and -negative cases detected in the study arm, the odds ratio (OR), hazard ratio - Cox proportional hazards regression (HR), relative risk (RR), relative benefit (RB) and absolute benefit (AB) indicators at 95%CI will be calculated.

The obtained results and indicators of treatment intervention effectiveness will be selected to consider the applicability of the study findings and the possibility of the study results translation into real-world clinical practice.

Data evaluation will be carried out continuously, immediately after they enter the registration form and the database. Preliminary statistical calculations and analysis for study evaluation and monitoring will be provided in several stages, when:

I - More than 50% of patients will be included in the study;

II - The study arms will be fully formed, and more than 50% of patients will complete a 3-month and a 6-month follow-up;

III - All study participants will be included in the study, and at a minimum, half of them will complete a 6-month and a 12-month observation period;

IV - All study participants included in the study will complete a 12-month follow-up.

The development of clinical endpoints will be monitored, and the relevant data will be collected in a special data registration form.

Observation and analysis of study activities, procedures, non-clinical outcomes and safety measures will be carried out continuously according to the monitoring and evaluation plan and procedures. Clinical case management processes in real-life medical care practice and factors that positively and negatively impact these processes will be assessed and characterized.

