Hypothesis	
The research question is how antiplatelet treatment for preventing major adverse cardiovascular events after ePCI works in chronic coronary artery disease when guided by personal genetic characteristics for drug metabolism.
 
The study aims to test two research hypotheses:
 
 
• CYP2C19 genotype-guided clopidogrel treatment ensures better clinical outcomes when compared with conventional treatment selection led without CYP2C19 genotyping.
 
• CYP2C19 genotype-guided antiplatelet treatment could be beneficially applied in real-world clinical practice.
 

Design	Multicenter, randomized, parallel-group controlled study

Primary Objectives	
The aim of the study is to evaluate CYP2C19 allele genotype-guided antiplatelet treatment outcomes.
 
The specific objectives of the study are:
 
 
— Pre-assignment and randomization of study participants into study arms for conventional and CYP2C19 genotype-guided antiplatelet treatment with clopidogrel or an alternative P2Y12 inhibitor;
 
— providing RT-PCR-based pre-, analytical and post-analytical processes of the study to ensure CYP2C19 *2, *3 allele profiling for detection of study participants with normal functioning (NFA) and loss of function (LOF) allele;
 
— Observation of clinical outcomes of patients in the study groups during the 12 months of treatment;
 
— Evaluation of processes and non-clinical outcomes of clinical case management;
 

Secondary Objectives	
 
— Implementation of the methods and procedures provided by the research protocol into a real clinical practice pipeline;
 
— Raising awareness and understanding of the role of laboratory services by bridging clinical, laboratory practice professionals and other stakeholders to achieve patient-centeredness and improve clinical outcomes;
 
— Evaluation of clinical practice models based on assessments of molecular markers;
 
— Disseminate study results through publishing a scientific paper in a peer-reviewed journal and abstracts for reporting study results.
 

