Study Participants	
240 patients requiring antiplatelet treatment with a P2Y12 inhibitor after ePCI as a major cardiovascular clinical event for CAD, meeting clinical inclusion criteria and not meeting exclusion criteria.

Randomization	
Inclusion in two parallel groups with a 1:2 allocation ratio of controls (active comparators) and experiments. Genotyping the CYP2C19 *2, *3 alleles of experimental arm participants for separation of carriers of normal *2, *3 function alleles (NFA) and Carriers of loss of function *2, *3 alleles (LOF).

Study arms	
3 arms of study participants:
 
1st arm - experimental: "Normal Metabolizers of Clopidogrel", 110 study participants diagnosed with chronic coronary artery disease who had undergone elective PCI, tested with CYP2C19 genotyping and identified as NFA *2, *3 carriers, who undergo CYP2C19 Genotype-Guided Clopidogrel Treatment - Clopidogrel as a component of preventive antiplatelet treatment such as double antiplatelet treatment (DAPT), or an antiplatelet drug (clopidogrel) combined with the non-vitamin K antagonist oral anticoagulants (NOAC), incl. triple antiplatelet treatment (Aspirin, Clopidogrel and a NOAC), or antiplatelet monotherapy (Clopidogrel).
 
2nd arm - experimental: "Passive Metabolizers of Clopidogrel", approximately‡ 50 study participants diagnosed with chronic coronary artery disease who had undergone elective PCI, tested with CYP2C19 genotyping, identified as LOF *2, *3 allele carriers, who undergo CYP2C19 Genotype Guided Antiplatelet Treatment Alternative to Clopidogrel - an antiplatelet drug alternative to clopidogrel in conventional dosing regimen, as a component of preventive antiplatelet treatment, such as double antiplatelet treatment (DAPT) with ticagrelor or prasugrel, or prasugrel combined with the nonvitamin K antagonist oral anticoagulants (NOAC), or antiplatelet monotherapy (ticagrelor, or prasugrel).
 
3rd arm - active comparator: "Unspecified Metabolizers of Clopidogrel", 80 participants diagnosed with chronic coronary artery disease who had undergone elective PCI were allocated to the arm, without CYP2C19 genotyping through simple randomization, and having an unspecified metabolism phenotype, who were assigned to the conventional

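### The only rank test named in section 2.6.3 is the Wilcoxon signed-rank test, a paired test that cannot compare the trial's independent, unequal arms; no rank-sum test is named anywhere

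*Combined protocol and SAP*

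**What the plan says.** Section 2.6.3 opens with descriptive statistics: the values and distributions of variables from the initial assessment and from follow-up "will be evaluated according to the experimental and control arms". The next paragraph turns to comparative analysis of quantitative variables, where "differences between the variable values will be calculated using the t-test or the Wilcoxon signed-rank test". The type of t-test is not given. The paragraph after that, on categorical variables, has the same construction: "differences between the variable values will be calculated using the chi-square or Fisher's exact tests".

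The Synopsis describes the design as a "Multicenter, randomized, parallel-group controlled study" and the randomization as "Inclusion in two parallel groups with a 1:2 allocation ratio of controls (active comparators) and experiments". Section 2.4.2 lists three contrasts: 110 normal metabolizers against 80 unspecified metabolizers, about 50 passive metabolizers against the same 80, and 110 normal against about 50 passive. Appendix 3 adds a contrast of the two genotyped arms pooled against the unspecified arm. For costs, Appendix 3 names Student's two-sample t-test.

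**The concern.** The signed-rank test ranks differences within matched pairs. Two arms made up of different people supply no such differences. A quantitative variable too skewed for a t-test would therefore have no usable test between arms under the plan as written. The analyst would have to substitute a test that the protocol does not name, possibly after seeing the data, or invent pairs. Invented pairs make the p-value depend on the order of the rows and leave part of the larger arm out.

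The variables exposed are the quantitative baseline characteristics collected under section 2.5.1 and the measures repeated under Appendix 2: echocardiography, HbA1c, blood count and creatinine/eGFR.

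**Working it through.** **1. What is being compared.** The only grouping that 2.6.3 names is the arm. Three things in the document point to comparisons between independent groups:

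- The categorical sentence mirrors the quantitative one and names chi-square and Fisher's exact tests, which in this form compare independent groups.
- The design is parallel-group, and no matching or crossover is described.
- The quantitative contrasts that Appendix 3 spells out, those for costs, use a two-sample t-test.

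**2. Whether the named test can be computed.** The arm sizes come from section 2.4.2; the pooled arm is 110 + 50 = 160. Given two columns of these unequal lengths, standard software returns an error for the signed-rank test at all four contrasts. If an analyst forced pairs, the number of pairs would be min(n1, n2) and the number left over |n1 − n2|:

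| Contrast | Pairs | Left over | Share of contrast |
|---|---|---|---|
| 110 v 80 | 80 | 30 | 30/190 = 16% |
| 50 v 80 | 50 | 30 | 30/130 = 23% |
| 110 v 50 | 50 | 60 | 60/160 = 38% |
| 160 v 80 (pooled) | 80 | 80 | 80/240 = 33% |

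**3. What forced pairing would do, as an illustration.** This was simulated with 3,000 runs, normal data and a two-sided 0.05 level. The effect is an assumed shift of 0.4 SD; neither the shift nor normality comes from the documents.

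| Contrast | Null rejection, rank-sum | Null rejection, forced-pair signed-rank | Power, rank-sum | Power, forced-pair signed-rank |
|---|---|---|---|---|
| 110 v 80 | 0.047 | 0.050 | 0.76 | 0.69 |
| 50 v 80 | 0.052 | 0.049 | 0.57 | 0.49 |
| 110 v 50 | 0.047 | 0.051 | 0.62 | 0.48 |
| 160 v 80 | 0.050 | 0.050 | 0.82 | 0.69 |

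The rank-sum test runs at every planned size with close to nominal error. Arbitrary pairing did not raise the false-positive rate here; its price is lost power and a result that depends on row order.

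**4. Whether the sample size is touched.** The plan's figure of at least 221 (section 2.6.2) is a two-proportion calculation: p1 = 0.6 (control), p0 = 0.4 (experimental), ratio k = 2, two-sided α = 0.05, power 0.8. With pooled p = (0.6 + 2 × 0.4)/3 = 0.467:

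n(control) = [1.96 × √(1.5 × 0.467 × 0.533) + 0.842 × √(0.24 + 0.24/2)]² / 0.2² = (1.198 + 0.505)² / 0.04 ≈ 72.5, rounded up to 73.

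The total is 73 + 146 = 219, within 2 of the stated 221. No rank test enters it.

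**5. Whether the endpoints are touched.** The primary, secondary and composite clinical endpoints in section 2.6.1 are numbers of participants with an event. They are analysed by chi-square or Fisher's exact test, odds ratio, relative risk and Cox hazard ratio, so this sentence does not reach them.

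**The case against.** The strongest reply is that the signed-rank test was meant for change within a patient. The sentence naming arms and the sentence naming the test sit in separate paragraphs, and the first is about descriptive statistics. That first paragraph also covers both initial and follow-up results and speaks of trends. Appendix 2 repeats echocardiography and HbA1c at screening, 6 and 12 months, and blood count and creatinine/eGFR at screening, 3, 6 and 12 months. For changes in these the signed-rank test is legitimate, so it would be wrong to say that the section mentions nothing but arms.

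This reply does not rescue the sentence. The sentence does not limit the test to within-patient change, and the parallel categorical sentence points the other way. If the within-patient reading is right, the plan has no non-parametric test between arms at all, and the unqualified t-test could be either paired or two-sample. The same sentence needs editing on both readings.

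Two further objections stand and limit the point. A t-test is offered as an alternative, so a route between arms exists when its assumptions are reasonable. And nothing in the plan proposes pairing patients across arms; because software stops at unequal lengths, the slip would probably be noticed.

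A reader might infer that the trial's efficacy comparisons are invalid, or that 30 to 80 participants will be lost from analysis. The documents support neither: the clinical endpoints use other methods, and the losses arise only if someone invents pairs. Nor does the point reach the cost comparisons, since Appendix 3 names an unpaired test for them.

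**Conclusion.** The point holds within a narrow scope. The only non-parametric test that 2.6.3 offers for quantitative variables is a paired one, the arms are independent and unequal, and no rank-sum test is named anywhere. As written, quantitative baseline and follow-up variables have no valid rank-based comparison between arms.

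This rests on reading the comparative sentence as covering comparisons between arms, which its context favours but its wording does not state. That the document names no rank test usable between arms does not depend on that reading. The counts left over under forced pairing follow from the planned arm sizes, with the passive arm taken as exactly 50, and remain hypothetical. The power figures also depend on the assumed 0.4 SD shift and normal data. The slip is worth correcting, but it does not threaten the trial's main results.

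**What to change.** In section 2.6.3, replace the signed-rank test with the Wilcoxon rank-sum (Mann-Whitney) test, alongside the two-sample (Welch) t-test, for comparing quantitative variables between arms. If change from baseline within a patient is also to be tested, say so and assign the signed-rank or paired t-test to that purpose only. Add the rule for choosing between the t-test and the rank test, fixed before the arms are compared.

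This costs a sentence or two of text. It needs no extra participants, visits or data, and it leaves the sample size, the endpoint analyses and the cost comparisons in Appendix 3 as they are.
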